### **Intervention arms**

Participants in the two intervention groups (family-based mHealth intervention and mother-only mHealth intervention) will be granted free and unlimited access to the respective smartphone app from the time of recruitment up to four weeks after childbirth. Their usage of the app will be recorded in terms of the time spent on the app (in minutes). For ethical reasons, the participants in the intervention groups will not be deprived from usual face-to-face antenatal classes at the hospitals; instead, they will be provided something more than they can obtain in existing service.

### **Control arm**

The control group will receive routine services provided by KWH and TYH, i.e., they will be provided with information and videos about all the essential information for expectant parents via a smartphone app. They can be enrolled to nurse-led face-to-face antenatal classes, although 39% of first-time mothers previously reported that they were unable to join the face-to-face antenatal classes due to the limited seats available. For those who are not offered a place for the antenatal classes, they will not have the opportunity to ask questions about their pregnancy until their antenatal visits.

### **Follow up survey**

Participants will be contacted for the follow-up survey around four weeks after childbirth via their preferred contact method indicated in the baseline survey.

## **Measurements**

Specific outcome indicators and the target respondents are listed both in Table 2 and as follows:

### ***Primary outcome:***

*Symptoms of Maternal Pregnancy depression and PND at four weeks postpartum* will be assessed with the validated Chinese version of the 10-item Edinburgh Postnatal Depression Scale (EPDS).

### ***Secondary outcomes:***

*Perceived social support levels of expectant mothers* will be assessed with the Chinese version of the 12-item Multidimensional Scale of Perceived Social Support (MSPSS).

*Anxiety and stress levels of all participants* (including the expectant mother, father, and grandparents) will be assessed with the Anxiety and Stress subscales of the Chinese version of the Depression Anxiety Stress Scale (DASS21).

*Health-related quality of life (QoL) of all participants* will be measured with the validated Chinese version of the Short-form-12 Health survey (SF-12 v2), which consists of 12 items to be computed as two composite scores: physical component score and mental component score.

*Perceived family cohesion levels of all participants* will be assessed using the nine-item Family Cohesion subscale of the Chinese version of the Family Environment Scale. Sample questions include: “Family members really help and support one another”, “We put a lot of energy into what we do at home”, and “We often seem to be killing time at home”. Each item is rated on a 6-point scale, ranging from 1 = strongly agree to 6 =strongly disagree. The scale showed adequate reliability and validity in a previous study in a Chinese sample.

### **Covariates**

Demographic information including age, education level, marital status, family monthly income adjusted for household size, number of children, and family living arrangement will be collected.

Service utilisation: App users' feedback and engagement data will be obtained via: 1) participants' self-reported usage of the app and 2) the app itself which will capture users' usage of the app, in terms of frequencies and duration of access. For all participants, information about their utilisation of services, such as participation in face-to-face antenatal classes, usage of other similar app and resources on pregnancy care, etc. will be collected via the self-report questionnaire.

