The literature shows that involving fathers in different stages of pregnancy and childbirth may have positive impacts on promoting family health and improving marital relationships. In a local study, an intervention programme called Positive Fathering was successfully in improving physical health, mental health, and marital relationship of expectant fathers. These positive outcomes in fathers may have potential benefits to expectant mothers, which may in turn, improving overall family health.

Engaging and educating expectant grandparents is equally essential to enhance pregnancy support, especially in Hong Kong households. In Hong Kong, approximately 30% of grandparents were living with young children more than five days a week, and more than 25% were responsible for providing primary childcare during the daytime. Grandparental involvement in pregnancy and childcare has been demonstrated to improve family health and reduce PND by increasing the levels of perceived social support among mothers, and promoting a healthy and non-violent family environment.

Possible mechanisms underlying the positive impacts of father and grandparent involvement may include increased social support, improved knowledge on pregnancy, and enhanced family communication and relationships. In a study on social capital during pregnancy, it was shown that close family was one of the most important sources of social capital that significantly influences maternal health other than medical professionals. As the immediate environment that expectant mothers primarily inhabit, the family could provide valuable psychosocial resources through strong family cohesion.

In the proposed study, we aim to develop and test a new mHealth intervention by including a smartphone app with different versions specifically designed for expectant mother, father, and grandparents who are part of the same household. To our best knowledge, there has been no empirically evaluated family-based mHealth intervention for pregnancy support.

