**Sample size calculation**

Assuming a Cohen's d effect size of 0.20, an effective sample of 1,182 would be required to achieve 80% statistical power in detecting the effect in pairwise comparison. Assuming a retention rate of 75% for the current sample, a total of 1,578 families will be recruited.

(ii) **Implementation Plan**

This project will involve development, implementation and evaluation of the family-based mHealth intervention. Details of the development and implementation of the intervention are elaborated below, and the evaluation of the intervention is detailed in Section (v).

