### **Randomization**

The RCT will require recruitment of three groups, on a 1:1:1 basis, for comparison: (i) mother-only mHealth intervention; (ii) family-based mHealth intervention; and (iii) health information control. A computerized blocked randomisation programme will be used to generate a series of random numbers to determine the group to which the family is assigned.

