### **Ethical consideration**

Approval for the ethics of this study has been obtained from the institutional review boards of the respective institutions. Participation in the study will be completely voluntary. Participants will be reminded that they have the right to terminate their participation at any time during the study, and this will not affect the standard of care they receive at the hospital. All personally identifiable information will be removed before data analysis. In this study, we will obtain information about participants' symptoms of pregnancy depression and PND via the self-reported EPDS at baseline and follow-up. For mothers whose EPDS score is equal to or higher than the cut-off score of 10, we will encourage them to seek help from health and social services. All mothers will receive regular health services and treatments in the hospital as usual. The only difference between the intervention groups and the others will be the use of the mother-only mHealth intervention app or the family-based mHealth intervention app. We will remind mothers that there are relevant services (e.g., the Comprehensive Child Development Service) in the routine hospital care that they can approach when in need.

(vi) **Results analysis**

With regards to **Objective (i)**, we will conduct descriptive analyses to obtain the usage and the coverage of the intervention.

To fulfil **Objectives (ii) and (iii)**, we will conduct general linear model (GLM) to analyse the data. In each GLM, we will use one outcome indicator measured in the follow-up survey as the dependent variable, the corresponding outcome indicator in the baseline survey as the covariate, and the group (family-based mHealth intervention, mother-only mHealth intervention, control [referent group]) as independent variable. We will also conduct sub-group analyses to explore whether the effectiveness of the family-based intervention is affected by various demographic or family factors.

All statistical analyses will be conducted with the intention-to-treat principle. All missing data will be treated with multiple imputation method or full information maximum likelihood depending on the analysis model. Nonetheless, analysis will be performed to compare any baseline differences between dropouts and retained participants. The baseline difference will also be examined by descriptive statistics. SPSS 20.0 will be used, and two-tailed p-values  $< .05$  will be regarded as statistical significance.

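### The baseline factors headed 'Covariates' are absent from the outcome model, which gives up a small gain in precision that would cost almost nothing

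*Combined protocol and SAP*

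**What the plan says.** The Covariates section has two parts. The first lists demographic and family factors: age, education, marital status, income adjusted for household size, "number of children, and family living arrangement will be collected". The second, on service utilisation, covers app engagement recorded by the app and by self-report, and for all participants "participation in face-to-face antenatal classes, usage of other similar app and resources on pregnancy care".

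The outcome model is in section (vi), Results analysis. The follow-up score is the dependent variable, group is the independent variable, and "the corresponding outcome indicator in the baseline survey as the covariate" is the only adjustment. The same section uses demographic and family factors to explore subgroups, compares dropouts with retained participants at baseline, and describes baseline differences. It assigns app usage to descriptive analysis under Objective (i), states intention to treat, and handles missing data by multiple imputation or full information maximum likelihood (FIML) without naming the variables involved.

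Hospital appears neither under Covariates nor in the model, although two hospitals recruit.

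**The concern.** A section headed Covariates would normally supply the adjustment set. Here nothing in it enters the effectiveness model, and a reader cannot tell whether it is meant for adjustment or is only a data-collection list.

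The factors are recorded in any case. Entry is not limited to first-time mothers, and co-residence is not an eligibility criterion, so number of children and living arrangement will vary between families. If such factors predict the follow-up score, adjusting for them narrows the standard error of every contrast and removes the effect of chance imbalance in them. With 25% loss expected, conditioning on them also makes the missing-at-random assumption easier to defend. The stake is efficiency, not validity: omitting a prognostic baseline factor from a randomised comparison does not bias this model's group contrast.

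**Working it through.** **Inputs.** From Sample size calculation: "Assuming a Cohen's d effect size of 0.20, an effective sample of 1,182 would be required". The target there is 80% power for each pairwise contrast, with 75% retention and 1,578 families recruited. From Results analysis: "two-tailed p-values $< .05$ will be regarded as statistical significance". From Randomization: "The RCT will require recruitment of three groups, on a 1:1:1 basis, for comparison". The variance explained by the demographic factors, and the correlation between baseline and follow-up EPDS, are not given. Both are assumed below and shown over a range.

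**Step 1: reproduce the plan's figure.** By the normal approximation, n per arm = 2(1.960 + 0.842)²/0.20² = 392.4, so 393 per arm and 1,179 in three arms. The t-test version gives 393.4, so 394 per arm and 3 × 394 = 1,182, as stated. For dropout, 394/0.75 = 525.3, so 526 per arm and 3 × 526 = 1,578, as stated. Neither figure takes credit for any covariate.

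**Step 2: size the gain.** Let ρ be the correlation between baseline and follow-up score, and R² the share of the remaining variance that the added factors explain. The residual SD is multiplied by √[(1 − ρ²)(1 − R²)], so

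power = Φ( 0.20 × √(394/2) / √[(1 − ρ²)(1 − R²)] − 1.960 ).

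With ρ = 0 and R² = 0 this is Φ(2.807 − 1.960) = 80.2%.

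| Assumed ρ | R² = 0 | R² = 2% | R² = 5% | R² = 10% |
|---|---|---|---|---|
| 0 (basis of the planned calculation) | 80.2% | 80.9% | 82.1% | 84.1% |
| 0.3 | 83.7% | 84.4% | 85.5% | 87.3% |
| 0.5 | 90.0% | 90.6% | 91.4% | 92.7% |

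Before rounding, the gain from R² = 2% to 10% is 0.8 to 4.0 points in the first row, 0.7 to 3.6 in the second and 0.6 to 2.7 in the third. The standard error is multiplied by √(1 − R²), which is 0.990, 0.975 or 0.949. In the first row, the evaluable total needed for 80% power (normal approximation) falls from 1,179 to 1,155, 1,119 or 1,062.

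The first row applies if d = 0.20 is already on the residual scale, the others if it is on the raw scale. The plan does not say which. The exclusion of mothers scoring 10 or more on the EPDS at entry narrows the range of the baseline score and may lower ρ, but by how much cannot be worked out from the documents.

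**Step 3: size the cost.** With 1,182 evaluable families, the planned model leaves 1,182 − 4 = 1,178 residual degrees of freedom (intercept, two group terms, baseline score). Adding k columns with no prognostic value would inflate the variance of a contrast by roughly k/1,178. If hospital, age, income and number of children take one column each, and education, marital status and living arrangement two each (assumed coding), k = 4 + 6 = 10 and the inflation is about 10/1,178 = 0.8%. The factors therefore pay for themselves once R² exceeds about 0.8%, which is below the bottom of the assumed range. The table does not deduct this cost.

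**The case against.** Adjusting for the baseline score alone is an accepted, prespecified analysis, and that score is usually the strongest predictor available. The rest may add little, and no R² is documented. The rationale in section (b)(iii), that grandparental involvement may "reduce PND by increasing the levels of perceived social support among mothers", describes a mechanism of benefit. It does not say that age, education, income or living arrangement predict EPDS. Baseline factors can also enter multiple imputation as auxiliary variables without being in the outcome model. All of this stands, and it is why the point is one of modest efficiency. It does not remove the reason to act, because the variables are already collected and the cost is slight.

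A reader might go further and infer from the shared heading that the plan invites adjustment for app use, and that this would erase the treatment effect. The documents do not support that. Results analysis names a single covariate, gives app usage a descriptive role and states intention to treat. No section proposes such an adjustment.

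Nor is erasure the necessary result if someone did it. In an illustrative simulation with a true effect of −0.20 SD and no confounding of use with outcome, the adjusted effect was about −0.15, −0.10, −0.05 or 0.00 SD when use carried 25%, 50%, 75% or 100% of the effect. With confounding it ranged from −0.25 to +0.10. Such an adjustment would not estimate the intention-to-treat effect, but it is not in the plan. The Covariates section also does not say at which survey self-reported service use is collected; only in-app use is certain to follow randomisation.

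**Conclusion.** The point holds as a low-cost improvement in precision. The factors headed Covariates have no role in the effectiveness model, and adding them would be worth about 1 to 4 power points at an assumed partial R² of 2% to 10%. If baseline EPDS correlates 0.5 with follow-up, also an assumption, the gain is about 0.6 to 2.7 points, starting from 90.0%.

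Three stronger readings should be set aside. The omission does not bias the comparison. It does not leave the trial under-powered against its own calculation. And the factors are not wholly unused, since the subgroup analyses and baseline checks draw on them. The placing of app and service use under the same heading is a labelling matter only.

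**What to change.** In Results analysis, prespecify each model as follow-up score on group, baseline score, hospital and the pre-randomisation factors in the Covariates section: the respondent's own age, education and marital status, with income, number of children and living arrangement. Using the respondent's own values matters because fathers and grandparents also have outcomes. Fix the coding in advance. Keep the baseline-score-only model as a sensitivity analysis, and name the same factors in the imputation or FIML model.

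As a clarification, move app and service use to a separate process-measures heading and state that they do not enter the main intention-to-treat model. Secondary mediation or complier analyses need not be barred.

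The change is to wording. No new data are needed apart from recording hospital as a model term, and the statistical cost is a few degrees of freedom out of about 1,180.

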### **Ethical consideration**

Approval for the ethics of this study has been obtained from the institutional review boards of the respective institutions. Participation in the study will be completely voluntary. Participants will be reminded that they have the right to terminate their participation at any time during the study, and this will not affect the standard of care they receive at the hospital. All personally identifiable information will be removed before data analysis. In this study, we will obtain information about participants' symptoms of pregnancy depression and PND via the self-reported EPDS at baseline and follow-up. For mothers whose EPDS score is equal to or higher than the cut-off score of 10, we will encourage them to seek help from health and social services. All mothers will receive regular health services and treatments in the hospital as usual. The only difference between the intervention groups and the others will be the use of the mother-only mHealth intervention app or the family-based mHealth intervention app. We will remind mothers that there are relevant services (e.g., the Comprehensive Child Development Service) in the routine hospital care that they can approach when in need.

(vi) **Results analysis**

With regards to **Objective (i)**, we will conduct descriptive analyses to obtain the usage and the coverage of the intervention.

To fulfil **Objectives (ii) and (iii)**, we will conduct general linear model (GLM) to analyse the data. In each GLM, we will use one outcome indicator measured in the follow-up survey as the dependent variable, the corresponding outcome indicator in the baseline survey as the covariate, and the group (family-based mHealth intervention, mother-only mHealth intervention, control [referent group]) as independent variable. We will also conduct sub-group analyses to explore whether the effectiveness of the family-based intervention is affected by various demographic or family factors.

All statistical analyses will be conducted with the intention-to-treat principle. All missing data will be treated with multiple imputation method or full information maximum likelihood depending on the analysis model. Nonetheless, analysis will be performed to compare any baseline differences between dropouts and retained participants. The baseline difference will also be examined by descriptive statistics. SPSS 20.0 will be used, and two-tailed p-values  $< .05$  will be regarded as statistical significance.

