**Objectives**

- (i) To develop a family-based mHealth intervention to engage family members in supporting expectant mothers during pregnancy;

- (ii) To evaluate the effectiveness of the family-based mHealth intervention in reducing PND and promoting health (symptoms of depression, anxiety, and stress, health-related quality of life, and social support) among expectant mothers; and
- (iii) To evaluate the effectiveness of the family-based mHealth intervention in promoting the health (symptoms of anxiety and stress, and health-related quality of life) of the expectant fathers and grandparents and promoting family cohesion.

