### **Baseline survey**

Participants will be briefed by a trained research assistant about the purpose and the details of the study, and will be asked to provide written consent. Blocked randomisation will be performed using a centralised online website upon participation. Depending on their group assignment, expectant mothers will be asked to download the respective smartphone app, log in to the app with a unique username and password that they will be assigned. The expectant mothers will also be asked to complete the baseline survey via online, which will take about 15-20 minutes to complete. After that, the participants will be asked about their expected delivery date, and their preferred contact method for the follow-up survey.

Eligible expectant fathers and grandparents who are not present at the clinics will be contacted by the research assistant using the contact methods given by the participating mothers, study details will be explained to them, and they will be asked to provide informed consent. They will be instructed to complete a structured questionnaire, which will take about 15 minutes. Fathers and grandparents who are

allocated to the family-based intervention group will then be provided with a link to download the father or grandparent version of the app, and a unique login information.

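### Families are randomised, but the planned GLM has no family term, so any model holding two or more members of a family will understate its standard errors if members are positively correlated

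*Combined protocol and SAP*

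**What the plan says.** The Randomization section allocates families 1:1:1 to three arms, using random numbers to "determine the group to which the family is assigned". Every member of a family is therefore in the same arm.

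Objective (iii) concerns "promoting the health (symptoms of anxiety and stress, and health-related quality of life) of the expectant fathers and grandparents and promoting family cohesion". Under Secondary outcomes, anxiety and stress are measured on all participants ("including the expectant mother, father, and grandparents"), SF-12 is also measured on all participants, and so are "Perceived family cohesion levels of all participants". The Baseline survey section adds that "Eligible expectant fathers and grandparents who are not present at the clinics will be contacted by the research assistant". No section limits the number of grandparents per family.

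Section (vi) Results analysis gives one model for objectives (ii) and (iii), a general linear model: "In each GLM, we will use one outcome indicator measured in the follow-up survey as the dependent variable". Its other terms are the baseline value of the same outcome and the group. There is no random effect, GEE, clustered standard error or family-level summary. The section does not say whether models are fitted by role or over pooled roles, how many grandparents per family enter a model, or how several cohesion ratings of one family are combined.

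**The concern.** An ordinary linear model treats its records as independent given the covariates. Relatives in one family share a household history, a birth and, by design, an arm. The plan's own rationale treats the family as the expectant mother's immediate environment, and the family-based app adds shared messaging and a shared calendar. Positive correlation is therefore plausible. It is most plausible for cohesion, where several people rate the same family.

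Because the arm is constant within a family, positive residual correlation makes the model's standard error for the group effect too small. Confidence intervals are then too narrow and p < .05 is too easy to reach. Hypothesis (ii), on fathers, grandparents and family cohesion, would rest partly on such tests, so a false claim of benefit for grandparents or for cohesion becomes more likely.

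**Working it through.** **The plan's sample size, reproduced.** Inputs from Sample size calculation: d = 0.20, 80% power, pairwise comparison, 75% retention. Two-sided alpha of 0.05 is taken from Results analysis. The two-sample t-test calculation gives 394 per arm, and 394 × 3 = 1,182. Then 394/0.75 = 525.3, rounded up to 526, and 526 × 3 = 1,578. Both stated figures are reproduced. They count families, with one record each.

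**Formulas.** Let m be the records per family in one model and r the within-family correlation of residuals after baseline adjustment. The documents give neither, so both are assumed.

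- Design effect: DE = 1 + (m − 1)r
- Unequal family sizes: DE = 1 + r(Σm²/Σm − 1)
- Naive SE / true SE = 1/√DE
- Actual two-sided type I error = 2[1 − Φ(1.96/√DE)]

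For half the families with one grandparent and half with two, Σm²/Σm = 2.5/1.5, so DE = 1 + 0.667r.

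| Records per family | DE (r = 0.1 / 0.3) | SE too small by | Actual type I error |
|---|---|---|---|
| 1 | 1.00 / 1.00 | 0% / 0% | 5.0% / 5.0% |
| half 1, half 2 | 1.067 / 1.20 | 3.2% / 8.7% | 5.8% / 7.4% |
| 2 | 1.10 / 1.30 | 4.7% / 12.3% | 6.2% / 8.6% |
| 3 | 1.20 / 1.60 | 8.7% / 20.9% | 7.4% / 12.1% |
| 4 | 1.30 / 1.90 | 12.3% / 27.5% | 8.6% / 15.5% |

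**Does baseline adjustment remove the correlation?** Only in part. Suppose the raw correlation is 0.3, the family component is the same at both visits, and the baseline to follow-up correlation is 0.5. Then the residual correlation is 0.3 × (1 − 0.5)/(1 + 0.5) = 0.10. That corresponds to the r = 0.1 figures: 6.2% for m = 2 and 8.6% for m = 4.

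**Simulation check.** The planned baseline-adjusted model was simulated with two arms of 394 families, no true effect, r = 0.3 and 3,000 runs. It rejected in 5.1%, 8.9%, 11.5% and 14.4% of runs for m = 1, 2, 3 and 4. With family-clustered standard errors the rates were 5.1%, 5.4%, 5.3% and 4.7%. The formula and the remedy are both confirmed.

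**Power with correct standard errors.** If all 394 families per arm contribute two records, the effective number per arm is 394 × 2/DE. Power at d = 0.20 is then 0.966 (r = 0.1) or 0.936 (r = 0.3), so this correction needs no more families.

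**The case against.** The strongest reply is that no pooled model is written down. The objectives separate mothers from relatives, the app has role-specific versions, and each model takes one indicator with its own baseline, so analysis by role is a natural reading. On that reading, mother and father models have one record per family and nothing is wrong with them. This is right as far as it goes, but the plan does not say it. Nor would it protect a grandparent model in which any family supplies two grandparents.

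The evidence for several grandparents per family is indirect. The plural in the Baseline survey section proves little, since fathers are plural there too. The Secondary outcomes wording is better evidence: it sets a singular mother and father beside plural grandparents. More than one is clearly allowed, but no number is given.

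The size is also open to challenge, because m and r are assumed. The plan reports smartphone penetration of 58% to 70% over age 60, requires a smartphone and email address of each participating member, and expects 75% retention. Multi-grandparent families may therefore be a minority. If 25% of contributing families had two grandparents and the rest one, Σm²/Σm = 1.75/1.25 = 1.4. DE is then 1.04 to 1.12 and type I error 5.5% to 6.4% for r = 0.1 to 0.3. This stands: the grandparent-only case may be modest, and the top of the range needs four records from every family in one model.

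Table 2, on target respondents, is not in the text available. The plan says its content is also listed in the text, so it is unlikely to specify a model. The remark that missing-data handling depends on the analysis model names no alternative, and subgroup analyses by family factors address effect modification, not dependence.

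**Conclusion.** The concern holds, on two conditions: that a family contributes at least two records to a model, and that their residuals are positively correlated. Where both are met, the stated model gives standard errors that are too small, whatever the exact values.

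The inflation runs from nil with one record per family to about three times the nominal level (15.5%) with four records and a residual correlation of 0.3. The likelier grandparent cases lie near the lower end, at roughly 5.5% to 8.6%. Larger inflation would come mainly from pooling cohesion or other outcomes over several members.

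Maternal EPDS, MSPSS, mother-only and father-only models, and the figures of 1,182 and 1,578 families are unaffected. This is a correction that should be made to the secondary analyses; it does not threaten the primary comparison.

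**What to change.** The essential change in section (vi) Results analysis is one rule: any model in which a family contributes more than one record uses a linear mixed model with a random family intercept, GEE, or family-clustered standard errors, with a role term if roles are pooled. The simple GLM stays where there is one record per family.

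Three clarifications make the rule workable:

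- state that models are fitted separately by role unless specified otherwise;
- state whether cohesion is analysed by role, as a family mean, or pooled under the rule above;
- state how many grandparents per family may enter a model, or that one is nominated in advance.

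As a refinement, any multiple imputation feeding a clustered model should reflect the family level.

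The cost is a few sentences and a little more analysis work, with no change to data collection or to the number of families. Confidence intervals for grandparent and pooled cohesion outcomes will be somewhat wider. If every family gives two records, they widen by a factor of √1.10 = 1.05 to √1.30 = 1.14 for residual correlations of 0.1 to 0.3.
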